Positive psychology therapy group will be intervened by a psychotherapy developed from an American psychologist. The positive psychology therapy lasts 8 weeks, and has a group intervention in each week. The themes of each week are start-up, time gift, positive mind, three good things, a thankful heart, life train, active service, end-up.

Resilience promotion therapy group will be intervened by another psychotherapy developed by the researchers. The resilience promotion therapy lasts 8 weeks, and also has a group intervention in each week. The themes of each week are start-up, mutual help, trust in yourself, thanksgiving feedback, care for yourself, emotional management, end-up.

Controlled routine activity group will have routine service delivered by social workers. This group will have routine service delivered by social workers.

Period(s) *

There is only one stage in the study.

Period Title *

Overall Study.

Started *

There will be 150 participants initiating the intervention.

Those 150 participants will be randomly assigned to three groups with around 50 participants in each group.

Completed *

We will do follow-up, and the number in each follow-up will be recorded.

Milestone Title [*]

Before the intervention, we will measure the participants, , and the stage is defined as T0.

We will do follow-up immediately after intervention, 3-month after intervention, 12-month after intervention, defined as T1, T2, T3 respectively.

Reason Not Completed Type [*]

We will record the exact reason (Adverse Event) why participants do not complete the study. The reason may be death, lack of efficacy, lost to follow-up, illness, withdrawal by subject or others.

2. Baseline Characteristics

Arm/Group Information *

Chi-square test will be applied to figure out the difference of enumeration data among three groups. ANOVA will be applied to test the difference of measurement data among three groups. F values and χ^2 values will be displayed to show the baseline data are no different in three groups.

Arm/Group Title *

Positive psychology therapy group

Resilience promotion therapy group

Controlled routine activity group

Arm/Group Description *§

All the recruited participants will be numbered and randomly allocated into three groups by random number table. The grouping results will be announced to the participants according to the random number table.

Overall Number of Baseline Participants *

There will be 150 participants initiating the intervention.

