Baseline Measure Information *

A group of demographic characteristics will be measured in the study, including gender, age, marital status, income per month, gender of lost kid, length of lost kid.

Baseline Measure Title *

- Age * : Continuous(years)
- Gender * : Female, Male
- Marital status: with a spouse, without a spouse
- Income per month: Categorical:
 - <=1000 RMB
 - >1000 and <2000 RMB
 - >=2000 RMB
- Gender of lost kid: Female, Male
- Length of lost kid: Continuous(years)

Measure Type *

- Count of Participants: Gender, Marital status
- Mean: Age, Length of lost kid
- Number: Gender of lost kid, Income per month

Measure of Dispersion *

- Standard Deviation
- Inter-Quartile Range
- Full Range

Baseline Measure Data *

The value(s) for each baseline measure, for each group and overall cannot obtain right now since the study has not been started.

3. Outcome Measures

Outcome Measure Information *

A questionnaire will be used during each measurement, including several scales in it. The saliva test of Dehydroepiandrosterone will also be done in each measurement.

Outcome Measure Type *

- Primary

Outcome Measure Title *

- Psychological resilience: a kind of ability to bounce back from adversity measured by Connor-Davidson Resilience Scale (CD-RISC). It is a self-reported scale by adding up 25 items and the total score ranges from 0-100, with higher score reflects higher resilience. The differences within two times frame are the changes of psychological resilience
- Depression: depressive mood in recent two weeks measured by Zung Self-rated Depression Scale (SDS). It is a self-reported scale by adding up 20 items and the total score ranges from 20-80, with higher score reflects higher depression. The differences within time frames are changes of depression
- Subjective well-being: a feeling of happiness measured by Campbell Index of well-being (IWB). It is a self-reported scale by adding up 8 items and the total score ranges from 2.1-14.7, with higher score reflects higher subjective well-being. The differences within time frames are change of subjective well-being
- Social avoidance: the phenomenon that a person is absent from normal social interaction with others measured by Social Avoidance and Distress Scale(SAD). It is a self-reported scale by adding up 14 items and the total score ranges from 0-14, with higher score reflects social avoidance. The differences within time frames are the changes of social avoidance

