- Sleeping quality: a reflection of one's mood in recent month measured by Pittsburgh sleep quality index(PSQI). It is a self-reported scale, with total score higher than 19 reflects sleeping disorder. The differences within each time frames are the changes of sleeping quality
- Post traumatic growth: the positive growth after an adversity measured by Post Traumatic Growth Inventory(PTGI). It is a self-reported scale by adding up 24 items and the total score ranges from 0-120, with higher score reflects more growth. The differences within time frames are changes of post-traumatic growth
- Health care behavior: a person's self-care behavior measured by Health Promoting Lifestyle Profile-II(HPLP-II). It is a self-reported scale by adding up 40 items in four dimensions. The total score ranges from 40-160, with higher score reflects better health care behavior. The differences within time frames are changes of health care behavior
- Concentration of dehydroepiandrosterone in saliva: a kind of hormone that reflects the person's psychological stress collected by Sarstedt saliva collection tube by chewing the sterile cotton strips for 60 seconds. It will be tested by enzyme-linked immunosorbent assay (ELISA) with Kit Number of HT81012 and Origin site in Canada PLLabs

Outcome Measure unit *

The psychological resilience, depression, subjective well-being, social avoidance, sleeping quality, post traumatic growth, and health care behavior are measured by scales with no unit.

Dehydroepiandrosterone has its concentration unit of pg/ml.

Outcome Measure Time Frame *

There will be four measurements, before the intervention, immediately after intervention, 3-month after intervention, and 12-month after intervention. They are defined as T0, T1, T2, T3 respectively.

Analysis Population Information

Overall Number of Participants Analyzed *

There will be 150 participants totally enrolled in the study.

Outcome Measure Data Table

Measure Type *

- Mean

Measure of Dispersion/Precision *

- Standard Deviation

Outcome Data *

The measurement value(s) for each outcome measure cannot obtain right now since the study has not been started.

Statistical Analysis Overview

Comparison Group Selection [*]

We will compare three groups' data.

Type of Statistical Test [*]

- Superiority
- Other (descriptive analysis)

P-Value [*]

P-Value will be set at 0.05.

Method [*]

- ANOVA
- Chi-Squared
- t-Test, 2-Sided

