- Other: repeated measurement of variance analysis within different measurements among different groups

Estimation Parameter [*]

- Mean Difference (Final Values)

4. Adverse Event Information

Time Frame *§

The intervention lasts 8 weeks, and we will record the adverse event each week. Then we will do follow-up immediately after intervention, 3-month after intervention, and 12-month after intervention. we will record the adverse event at each follow-up.

Adverse Event Reporting Description [*]

We will add relevant information about adverse event after finishing the study.

Collection Approach for Table Default *§

- Systematic Assessment: The psychotherapist will routinely determine whether or not certain adverse events have occurred through regular investigator assessment during intervention and in each follow-up.
- Non-Systematic Assessment: Self-reporting by participants or occasional assessment by the psychotherapist.

Adverse Event Term *

The most possible adverse event may be the psychological discomfort because the participants are experiencing bereavement.

We will provide information for in three tables summarizing adverse events in each group, including all-cause mortality, serious adverse events, and other (not including serious) adverse events.

Organ System *

- Psychiatric Disorders

5. Limitations and Caveats

There may be several limitations.

We may not reach the target number of participants because the bereaved parents present social avoidance and may not interested in the intervention. We will invite social worker to help recruiting and make calls to all registered bereaved parents.

The measurements are mostly based on self-reported scales and may lead to unreliable data. We will give instruction before fulfilling the questionnaire to ensure the participants understood.

6. Certain Agreements

Are all PIs Employees of Sponsor? *

- No: The principal investigator is not an employee of the sponsor

There is no agreement between the agent(university) and the principal investigators. The principal investigators are graduate students in the university. The principal investigators (PIs) can discuss the results of the study at a scientific meeting or any other public or private forum, or to publish in a scientific or academic journal information concerning the results of the study.

7. Results Point of Contact

Name or Official Title *

Professor: [name]

Position title: Director of Nursing Psychology Research Center

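### Salivary DHEA, one of eight primary outcomes, is to be estimated as an unadjusted difference in final pg/ml values although every participant has a T0 measurement; adjust for T0, and treat a log-scale analysis as a conditional addition

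*Combined protocol and SAP*

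**What the plan says.** Section 3 (Outcome Measures) lists eight outcomes under the single type Primary. Seven are questionnaire scores. The eighth is described as "Concentration of dehydroepiandrosterone in saliva: a kind of hormone that reflects the person's psychological stress"; the assay is an immunosorbent one ("It will be tested by enzyme-linked immunosorbent assay (ELISA") and the unit is given separately: "Dehydroepiandrosterone has its concentration unit of pg/ml". On timing the section says "The saliva test of Dehydroepiandrosterone will also be done in each measurement", so DHEA is available at T0, T1, T2 and T3.

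One analysis template covers all eight outcomes: mean and SD as summaries; ANOVA, chi-squared and a two-sided t-test as methods; and "repeated measurement of variance analysis within different measurements among different groups". The estimation parameter is "Mean Difference (Final Values". On significance, "P-Value will be set at 0.05". On numbers, "Those 150 participants will be randomly assigned to three groups with around 50 participants in each group".

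Each of the seven scale entries adds that differences between time points are the changes of interest. The DHEA entry has no such sentence. Nowhere does the plan name a covariate, a transformation, a distribution check, or a rule for readings below the assay's detection limit. It gives no DHEA mean, SD or CV, and no power calculation.

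**The concern.** A difference in final values ignores what T0 says about each participant. Two things follow.

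- Stable between-person variation in DHEA stays in the error term, so the comparison is less precise than the collected data allow.
- Chance imbalance at T0 passes into the estimate. With 50 per group, the standard error of a T0 difference between two groups is √(2/50) = 0.20 SD. With T0 correlation ρ, a fraction ρ of any such imbalance is expected to reappear in the final-value difference.

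This matters more for DHEA than for the other outcomes. Section 5 concedes that most measurements are self-reported and may be unreliable, and DHEA is the one primary outcome to which that does not apply.

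A second question is the scale. A concentration cannot be negative, and a few high readings can weigh heavily on a mean over about 50 people. The plan neither chooses a scale for DHEA specifically nor says how the raw scale would be checked.

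**Working it through.** **Inputs from the documents.** About 50 per group in three groups; significance level 0.05; two-sided t-test; DHEA measured at T0 to T3. There is no stated power or effect size to reproduce.

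**Assumed inputs.** Distribution, CV, correlation ρ between T0 and follow-up DHEA, and 50 analysed per group. Ranges are shown because the documents give none of these.

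**1. Adjusting for T0.** With a linear relation, adjustment multiplies the residual variance by 1 − ρ², so the expected test statistic is divided by √(1 − ρ²). Take an effect that gives about 50% power unadjusted. In simulation with lognormal data at CV 0.3, raw-scale power for that effect was 48%. The corresponding expected statistic is 1.960 − 0.050 = 1.910, and power is Φ(statistic − 1.960).

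| ρ | 1 − ρ² | Adjusted statistic | Power by formula | Power by simulation | Equivalent sample size, 1/(1 − ρ²) |
|---|---|---|---|---|---|
| 0.3 | 0.91 | 2.002 | 51.7% | about 52% | ×1.10 |
| 0.5 | 0.75 | 2.205 | 59.7% | about 60% | ×1.33 |
| 0.7 | 0.51 | 2.674 | 76.2% | about 76% | ×1.96 |

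Under the lognormal assumption, adjustment raised power at every CV from 0.3 to 1.0 and every correlation from 0.3 to 0.7 tried, on both the raw and the log scale.

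**2. Compared with change from T0.** If variances are equal at both times, the relative variance is 1 for final values, 2(1 − ρ) for change and 1 − ρ² for adjustment. At ρ = 0.3, 0.5 and 0.7, change gives 1.40, 1.00 and 0.60; adjustment gives 0.91, 0.75 and 0.51. Adjustment has the smallest variance in each case.

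**3. Choice of scale.** Simulated two-sided t-tests, 50 v 50, unadjusted. In the lognormal and gamma runs the effect is the ratio that gives a nominal 80% on the log scale for lognormal data of that CV. In the normal and truncated-normal runs it is a shift of 0.56 SD.

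| Assumed shape | CV | Raw | Log | Log minus raw (points) |
|---|---|---|---|---|
| Lognormal | 0.2 | 78.6% | 79.3% | +0.7 |
| Lognormal | 0.5 | 74.6% | 78.9% | +4.3 |
| Lognormal | 1.0 | 65.2% | 79.2% | +14.0 |
| Gamma | 0.3 | 77.5% | 75.9% | −1.6 |
| Gamma | 0.5 | 73.3% | 68.5% | −4.8 |
| Gamma | 1.0 | 60.8% | 43.7% | −17.1 |
| Normal | 0.2 | 78.9% | 78.0% | −0.9 |
| Normal | 0.3 | 79.2% | 75.9% | −3.3 |
| Truncated normal | 0.5 | 76.3% | 69.5% | −6.8 |

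A rerun at CV 1.0 gave 67% raw v 80% log for lognormal data and 62% v 44% for gamma data. The ends of the range are therefore uncertain by about a point: a gain of about 13 or 14 and a loss of about 17 or 18.

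**4. Type I error.** With lognormal data and no effect, the raw t-test rejected in 4.3% to 5.0% of trials over CV 0.2 to 1.5.

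**The case against.** *The planned repeated-measures ANOVA already uses T0.* In part this is so. If T0 is one of the repeated measurements, the group-by-time term compares changes over time. But the plan does not say which term answers the question, and the only estimate it names is a difference in final values. Step 2 also shows that comparing change is less precise than adjusting for T0, and at ρ = 0.3 it is worse than ignoring T0 (1.40 v 1.00).

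*The entries are generic.* The estimation parameter covers all eight outcomes and no scale is named for DHEA. That stands, so the raw scale is the natural reading rather than an explicit choice for this outcome. It does not supply the missing adjustment.

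*The correlation is unknown.* It is. If T0 predicted nothing, adjustment would gain nothing and cost one residual degree of freedom.

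*A reader might go further* and infer that, because DHEA is bounded at zero, it must be right-skewed, and that taking logs therefore costs almost nothing and protects power. The documents do not support this. A zero bound establishes neither skewness nor lognormality, and no DHEA data are given. Right skew alone does not settle it either: gamma data are right-skewed, yet the log analysis loses power there. The cost is also more than a sentence of text, because logs need a rule for zero or below-detection readings and the target changes from a difference in pg/ml to a ratio of geometric means.

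**Conclusion.** The point holds for baseline adjustment. The stated DHEA estimate leaves T0 unused, and adjusting for it raises a power of roughly 50% to about 52%, 60% or 76% at ρ = 0.3, 0.5 or 0.7. Those figures rest on assumed lognormal values, CV 0.3, the raw scale, and 50 analysed per group.

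On scale, the conclusion is conditional. A log analysis gains about 0 to 13 points if values are lognormal (CV 0.2 to 1.0). It loses 1.6 to about 18 points if they are gamma-shaped with a proportional effect (CV 0.3 to 1.0), and about 1 to 7 points in the normal and truncated-normal cases tabulated. The documents cannot say which applies.

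It would be wrong to conclude that the raw-scale test is invalid. Its type I error holds, and a mean difference in pg/ml is a legitimate target. This is a modest improvement in precision and pre-specification, not a flaw that threatens the trial's conclusions.

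**What to change.** 1. For DHEA, replace the unadjusted final-value comparison with group differences at T1, T2 and T3 from a model adjusted for T0 DHEA: either ANCOVA at each time or a repeated-measures model with T0 as a covariate. Report adjusted mean differences in pg/ml with 95% CIs.
2. Pre-specify a supporting analysis of log DHEA adjusted for log T0, reported as geometric mean ratios with 95% CIs. Make it the primary DHEA analysis only if the sponsor has grounds, recorded before unblinding, to expect roughly lognormal values.
3. State in advance how zero and below-detection readings are handled.

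Cost: a short paragraph in the analysis section and no new data, since T0 saliva is already planned. Item 1 uses one degree of freedom and needs a statement on participants without a T0 sample. Item 2 reports a ratio beside the pg/ml difference and may be sensitive to the rule in item 3.

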Full study protocol and statistical analysis plan

Official Title of the study:

Implementation of a Community-based Resilience Promotion Program to

Only-child Loss Parents in China

Date of the document:

28th October 2017

Contents:

1. Participant Flow

2. Baseline Characteristics

3. Outcome Measures

4. Adverse Event Information

5. Limitations and Caveats

6. Certain Agreements

7. Results Point of Contact

1. Participant Flow

Recruitment Details

We will choose a community in Changsha, where principle investigators' institution located, to recruit the participants. This community has a number of around 260 only-child loss(OCL) parents, and has a social organization to serve the bereaved parents. The recruitment will start at Nov 1st 2017 and last around one week. The recruitment announcement will be distributed to the participants via social worker in their daily online chat group or through telephone call.

Pre-assignment Details [*]

We firstly will assess the recruited people to ensure meeting the inclusion and exclusion criteria. The inclusion criteria are made according to the official documents. OCL Family is one that has given birth to only one child but now has no living birth or adopted child, and the bereaved mother is older than 49 years (medically maximum age for fertility in China).

Those with serious mental disorders or physical illnesses who were not able to complete the intervention and evaluation questionnaire will be excluded.

Than the final enrolled participants can be sure and randomized assignment will be conducted.

Enrollment (total, anticipatory)	150			Record the number of the eligible and the excluded
Allocation (randomized)	Group A	Group B	Group C	Record the number of the received and the unreceived
	50	50	50	
Follow-up (immediately after intervention)				The numbers of each follow-up stages are uncertain by now. But in the latter research, we will record information of the lost and the continued.
Follow-up (3-month after intervention)				
Follow-up (12-month after intervention)				

Arm/Group Information *

There are three groups in the study.

Arm/Group Title *

Positive psychology therapy group= Group A

Resilience promotion therapy group= Group B

Controlled routine activity group= Group C

Arm/Group Description *§

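### Eight outcomes are all primary and tested across three arms at a flat 0.05, with no lead outcome, visit, contrast or multiplicity rule, so the false-positive risk is well above 5%

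*Combined protocol and SAP*

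**What the plan says.** All of this is in section 3 (Outcome Measures) unless noted.

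- **Outcome type.** Primary is the only entry; there is no secondary tier.
- **Outcomes.** Eight are listed under that type. Seven are scales: "The psychological resilience, depression, subjective well-being, social avoidance, sleeping quality, post traumatic growth, and health care behavior are measured by scales with no unit". The eighth is a biomarker: "Concentration of dehydroepiandrosterone in saliva".
- **Visits.** "There will be four measurements, before the intervention, immediately after intervention, 3-month after intervention, and 12-month after intervention". These are T0 to T3, so three are post-baseline. None is named as primary.
- **Comparison.** "We will compare three groups' data". The test type is superiority, with descriptive analysis also listed. No pairwise contrast is singled out.
- **Error rate.** "P-Value will be set at 0.05".
- **Methods.** ANOVA, chi-squared, two-sided t-test and "repeated measurement of variance analysis within different measurements among different groups". The list does not assign methods to outcomes or visits, and does not say which repeated-measures effect (group, time or interaction) is the test of interest.
- **Estimate.** The mean difference in final values, with no visit attached. The outcome list speaks of changes between time points.
- **Size** (section 1, Participant Flow). 150 participants, about 50 per arm. No power, effect size or standard deviation is given.

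The official title begins "Implementation of a Community-based Resilience Promotion Program to", which points to Group B. The design also includes a positive psychology arm (Group A) and a routine-activity control (Group C).

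**The concern.** A 0.05 threshold limits false positives to 5% for one test. With eight co-equal primary outcomes and no rule for combining them, each outcome gets its own 5% chance. A reader cannot tell beforehand which result will count as the trial's answer, and the headline outcome, visit and contrast could be chosen after the data are seen.

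A second issue is the contrast. A three-group test asks whether any arm differs from any other. It can be significant because of Group A alone, which would say nothing about the resilience program. A superiority trial should fix in advance which difference it sets out to show.

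**Working it through.** **What can be reproduced.** The plan's 0.05 is a setting, not a derived figure, and 150 comes with no power calculation. The check is therefore what the 0.05 rule delivers across the listed outcomes.

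**Inputs from the plan:** 8 primary outcomes, 3 arms of 50, T0 to T3, 0.05 per test.

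**Assumed, because the plan does not give them:** any significant primary result may be claimed; neither therapy works; no dropout; participants independent; equal correlation between outcomes (0 to 0.8) and between visits (0.5 or 0.7).

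**Independent tests.** The chance of at least one false positive in k tests is 1 - 0.95^k.

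- k = 8 (one test per outcome): 1 - 0.95^8 = 0.337.
- k = 8 x 3 = 24 (one per outcome and post-baseline visit): 1 - 0.95^24 = 0.708.

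**Correlated tests.** Simulation, 6,000 replicates per setting. The group-by-time F test has (3-1)(4-1) = 6 and (150-3)(4-1) = 441 degrees of freedom. Each cell gives the chance of at least one p<0.05 at visit correlation 0.5 / 0.7.

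| Reading of the methods list | Outcome corr. 0 | 0.5 | 0.7 |
|---|---|---|---|
| 8 group-by-time tests | 33.8 / 33.1% | 27.3 / 26.8% | 20.6 / 21.2% |
| 24 B-vs-C t-tests | 65.6 / 60.5% | 53.4 / 48.5% | 42.0 / 37.3% |
| Same, counting only results favouring B | 41.0 / 35.8% | 28.3 / 25.4% | 21.5 / 18.0% |
| 24 three-arm ANOVAs | 66.4 / 60.3% | 54.1 / 49.6% | 43.6 / 37.7% |

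At outcome correlation 0.8 the eight group-by-time tests give 17.1 / 16.9%. The other three rows come to about 29-36%, 14-18% and 30-37%. Testing the repeated-measures group effect instead of the interaction gives much the same for eight tests: 34% down to 17%.

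**The contrast.** Suppose only therapy A works, by an assumed 0.5 SD, and B equals C. For one outcome at one visit, the three-arm ANOVA has noncentrality 50 x 0.5^2 x 2/3 = 8.33. With 2 and 147 degrees of freedom it is significant 72.7% of the time. If the effect holds at T1 to T3, the group-by-time test is significant 75.1% of the time (visit correlation 0.5) or 94.6% (0.7). These are correct rejections, not false positives, but they carry no evidence about Group B.

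**The case against.** The best defence is that repeated-measures ANOVA is the intended outcome analysis. Section 2 (Baseline Characteristics) already uses ANOVA and chi-squared for baseline comparisons, so their reappearance in section 3 may only repeat that use. This has force, and the 24-test scenarios should be read as what the plan permits rather than what it prescribes. No B-vs-C contrast is written anywhere, so those rows are illustrations. But section 3 lists ANOVA and t-tests under outcome analysis without restricting them, and the eight-test case, at 17-34%, does not depend on them.

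A second point is that inflation arises only if any one significant result may be claimed. If all eight outcomes had to be significant, there would be none. That is correct, but the plan states neither rule. Listing descriptive analysis beside superiority does not help, because it does not say which outcomes are descriptive only.

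Third, the title does not prove that Group B is the sole focus; A and B are described as parallel therapy arms. That stands, and the choice of contrast belongs to the sponsor. The gap is that no choice has been made.

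Finally, all simulated figures assume independent participants. Both therapies are delivered in weekly groups, and the criteria do not exclude both parents of one family. The percentages are therefore indicative rather than exact.

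**Conclusion.** The concern holds and should be fixed before the trial starts. If any significant primary result may be claimed, the overall false-positive risk is about 17-34% on the mildest reading, at least three times the nominal 5%. It is about 49-54% at outcome correlation 0.5 if outcomes are tested visit by visit. Even counting only results that favour B over C, it is about 25-28% at that correlation.

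The exact size depends on correlations that the plan does not give. The conclusion does not, since every value examined from 0 to 0.8 leaves the risk well above 5%. Separately, no single pre-specified comparison answers the question in the title.

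**What to change.** Before recruitment:

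1. Name one primary outcome, one visit and one contrast. One example is CD-RISC total score, Group B vs Group C, at a visit the sponsor chooses, two-sided 0.05.
2. Relabel the other seven outcomes as secondary.
3. Test any further contrasts or visits in an order fixed in advance, and then the Holm-adjusted secondary family. Proceed only while every earlier step is significant.
4. Report everything else as estimates with confidence intervals and no claim of significance.

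The gate matters. With it, the simulated overall error is 3.7-5.2%, under the global null and three partial-null settings (4,000 replicates; outcome correlation 0, 0.5 and 0.7; visit correlation 0.6). With the primary at 0.05 and Holm over the other seven also at 0.05 but no gate, it is 6.4-10.2%. The ceiling there is 0.05 + 0.05 = 10%, so the excess is simulation noise.

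If the sponsor wants to keep all eight as primary, one pre-specified test each with Bonferroni or Holm adjustment also controls the error, provided the visit and contrast are named. The price is power. At Bonferroni's 0.05/8 = 0.00625, with 50 per arm, no dropout and an assumed 0.5 SD difference, power for a pairwise comparison falls from 70.5% to 40.7%.

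**Cost.** Wording only, with no extra participants or data. Under the gated plan seven outcomes lose primary status, some nominal p<0.05 results cannot be claimed, and a non-significant early step blocks formal claims on later ones. The document is dated 28 October 2017 and recruitment opens on 1 November, so time is short. If that date is missed, the rule should at least be fixed before anyone examines outcome data.

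### The plan does not say which repeated-measures term decides superiority or what role the pre-treatment visit T0 has; if the group main effect over T0-T3 decides, the effect is diluted by exactly 25% and power falls

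*Combined protocol and SAP*

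**What the plan says.** All references are to the combined protocol and SAP.

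- Section 3, Method, lists ANOVA, chi-squared, a two-sided t-test and "Other: repeated measurement of variance analysis within different measurements among different groups". No model terms, deciding term or covariate are given.
- Section 3, under Outcome Measure Time Frame, gives the visits: "There will be four measurements, before the intervention, immediately after intervention, 3-month after intervention, and 12-month after intervention". The labels T0 to T3 follow that order. T0 is listed with the other three visits and given no separate role.
- Section 3, Comparison Group Selection: "We will compare three groups' data". The type of test is superiority, and "P-Value will be set at 0.05".
- Section 3, Estimation Parameter, names a difference in means of final values. The questionnaire outcomes are also described as changes between time points.
- Section 1, Milestone Title, confirms that T0 precedes treatment: "Before the intervention, we will measure the participants".
- Section 2 describes the allocation: "All the recruited participants will be numbered and randomly allocated into three groups by random number table". It uses baseline data only to test whether the arms differ.

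**The concern.** The natural reading is that the repeated-measures ANOVA has four within-person levels and that T0 is one of them. Such an analysis gives three F tests, and the plan does not say which one carries the superiority claim.

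- **Group.** This compares each arm's mean over all four visits. At T0 the randomised arms differ only by chance, so a visit with no treatment effect is averaged in.
- **Group by time.** With three arms and four visits this has (3-1) x (4-1) = 6 degrees of freedom. It responds to any departure from parallel profiles and names neither the better arm nor the visit.
- **Time.** This is not a comparison of arms.

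Two things are at stake. A real effect could be understated or missed if the group test decides. And with three F tests available at 0.05, the deciding one could be chosen after the data are seen.

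**Working it through.** **Inputs from the documents.** About 50 per arm ("Those 150 participants will be randomly assigned to three groups with around 50 participants in each group"), four visits, T0 before treatment, significance level 0.05, two-sided for the t-test. The plan gives no power or derivation for its total of 150, so there is no stated figure to reproduce.

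**Assumptions, because the documents give none.** SD 1 at each visit; constant effect d = 0.5 SD at T1, T2 and T3; equal correlation r between all visits (compound symmetry), varied from 0.3 to 0.8; no dropout.

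**Step 1: dilution.** With visit effects (0, d, d, d), the four-visit mean difference is 3d/4 = 0.75d and the T1-T3 mean difference is d. For unequal effects d1, d2, d3 the two means are (d1+d2+d3)/4 and (d1+d2+d3)/3, and their ratio is again 0.75. This step needs no assumption about d or r.

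**Step 2: variance of the per-person summary.**
- Mean of T0-T3: (1+3r)/4. At r=0.5: 0.625.
- Mean of T1-T3: (1+2r)/3. At r=0.5: 0.667.
- Mean of T1-T3 adjusted for T0: (1+2r)/3 - r². At r=0.5: 0.667 - 0.25 = 0.417.

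**Step 3: pairwise test at r=0.5**, as effect / sqrt(2 x variance / 50).
- T0-T3: 0.375 / sqrt(2 x 0.625/50) = 2.37, power 65%.
- T1-T3, no covariate: 0.5 / sqrt(2 x 0.667/50) = 3.06, power 86%.
- T1-T3 adjusted for T0: 0.5 / sqrt(2 x 0.417/50) = 3.87, power 97%.

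**Step 4: interaction F test, three arms, only B works.** Non-centrality = 50 x (2/3) x (3/4) x d² / (1-r) = 6.25/(1-r), on 6 and 441 degrees of freedom. At r=0.5 this is 12.5, power 75%.

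**Step 5: range of r** (non-central t and F, two-sided 0.05, d = 0.5).

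| r | Pairwise, T0-T3 mean | Pairwise, T1-T3 mean, no covariate | Pairwise, T1-T3 adjusted for T0 | 6-df interaction, only B works |
|---|---|---|---|---|
| 0.3 | 77% | 92% | 96% | 58% |
| 0.5 | 65% | 86% | 97% | 75% |
| 0.6 | 60% | 82% | 98% | 85% |
| 0.7 | 56% | 79% | 99% | 95% |
| 0.8 | 52% | 76% | >99% | 99% |

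**Step 6: sample-size equivalent.** The ratio of non-centralities, T0-T3 to T1-T3, is 0.75(1+2r)/(1+3r): 0.63 at r=0.3, 0.60 at r=0.5 and 0.57 at r=0.8. Matching 50 per arm with T0 left out would take 50 divided by this ratio, about 80 to 88 per arm.

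**Step 7: sensitivity.** At r=0.5 the T0-T3 against T1-T3 powers are 47% and 68% for d=0.4, and 80% and 95% for d=0.6. If correlation instead decays with visit spacing (AR(1), d=0.5), they are 85% and 94% at r=0.3, 73% and 89% at r=0.5, and 62% and 81% at r=0.7. Adjusted for T0, AR(1) power is 93% to 97% for r from 0.3 to 0.8.

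**The case against.** A reader might infer that the plan's analysis does dilute the effect by 25%. The documents do not support that. The Method line names no deciding term and fits a group-by-time interaction at least as well as a group main effect. In the interaction T0 acts as the reference, and nothing is diluted. The description of outcomes as changes fits that reading too. The final-values parameter is not a mean over T0-T3, and a t-test or ANOVA at a single post-treatment visit is undiluted. All of this stands, so the 25% is conditional on the group main effect being used.

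A reader might also infer that deleting T0 from the response is free. It is not. At r of about 0.6 or more, the 6-df interaction can beat the T1-T3 comparison without a covariate: 85% against 82% at r=0.6 and 95% against 79% at r=0.7, if only B works. If A works half as well as B, the interaction is ahead at r=0.7 (85% against 79%) but not at r=0.6 (72% against 82%). At r=0.7 a contrast of the T1-T3 mean minus T0 has about 97% power, so keeping T0 as a level with change contrasts is also valid. Adjustment for T0 is nevertheless at least as strong throughout: at r=0.3 the change contrast has 73% and the adjusted contrast 96%.

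The objection does not remove the gap. The final-values parameter and the t-test are listed, but nothing says that they decide superiority. The interaction F, even where powerful, does not by itself support a claim that a particular arm is superior.

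**Conclusion.** The concern holds in conditional form. The plan leaves open both the role of T0 and the deciding term. If the group main effect over T0-T3 decides, the effect is diluted by exactly 25%, and pairwise power is lower at every correlation examined: by about 15 percentage points at r=0.3, 21 at r=0.5 and 24 at r=0.8, for d = 0.5 under compound symmetry. If the interaction decides, there is no dilution, but its power runs from 58% at r=0.3 to 95% at r=0.7 if only B works, and a significant result does not identify the better arm or the time.

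This is more than missing detail, because neither F test properly answers the stated superiority question. The 25% depends only on T0 preceding randomised treatment. Every power figure rests on the assumed effect size, correlation structure and absence of dropout.

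**What to change.** In section 3, Method:

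1. State that T0 is not a level of the response. Use it as a covariate, by ANCOVA or a mixed model on T1, T2 and T3.
2. Judge superiority from pre-specified 1-df between-arm contrasts (such as B-C, A-C and B-A) at one named time point or on the T1-T3 average. Choose one: three pairs at three visits would otherwise leave nine contrasts per outcome.
3. State that the group main effect over T0-T3 and the time main effect are not evidence of efficacy.
4. Do not drop T0 without using it as a covariate.

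The cost is analysis wording only: same visits, same data, same sample size. Under the assumptions above, the T0-adjusted contrast has 96% power or more for r from 0.3 to 0.8 under compound symmetry, and at least 93% under AR(1).
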